1. Determine any change in pain, fatigue and psychological well-being as a result of SKY in PCa patients.
2. Assess changes in some physiological parameters in response to SKY in the same subjects, compare these with those from Part 1, and assess whether these translate into clinical effects.

Subjects:

PCa patients that have been treated with radiotherapy will be recruited to the study (Winship Cancer Institute Clinic, contact person [name]).

Inclusion criteria: Age \geq 45 years; having finished radiotherapy at least two months ago; ability to speak/read English and give informed consent; having an interest in being part of a study to evaluate yoga-derived exercises and eager to practice some kind of relaxation exercise daily for 3 months.

Exclusion criteria: Having a diagnosis of psychiatric illness or other major illness in addition to PCa, such as other cancers, uncontrolled hypertension, lung disease, liver disease or heart disease.

Approval by the IRB Committee will be applied for. All participants will sign consent forms and throughout the study they will be treated according to the ethical guidelines, in addition to standard treatment for PCa. Participants will be informed that the data obtained in this study will be kept in a separate approved password controlled secure database at the Winship Cancer Institute of Emory University, and that the data from this database will be linked to the approved clinical database in the same institution. They will also be told that they participate by their free will and that they are free to leave the study whenever they wish without giving any reason for it and not risking any consequence for the standard treatment that they will receive.

The men will be randomly assigned to one of two groups:

1. No treatment control.
2. Healing Breath Program (SKY).

SKY includes gentle stretches (yoga postures), specific breathing exercises (see below), and cognitive coping and stressor evaluation strategies. SKY is traditionally understood to dissolve emotional distress and create the subjective experience of rest and well-being. The instructors in SKY are trained by the International Art of Living Foundation. The yoga intervention is held over 13 weeks: in Week 1, subjects will receive yoga instruction for approximately 3 hours daily on 5 consecutive weekdays, and in Weeks 2-13, subjects will attend yoga instruction once a week for about 2 hours.

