The breathing techniques that are part of SKY are: (a) Three-Stage Pranayama with Ujjayi or "Victory Breath", (b) three sets of Bhastrika or "Bellow's Breath", and (c) SK, and they are practiced in that order. The breathing practices are done in a sitting posture, either in a chair or on the floor. Eyes are kept closed throughout the sessions.

A total of 50 patients will be randomized into the two study arms. 20 subjects are aimed at in each group, but to account for drop-out/exclusion, 25 subjects will be recruited per group (to accommodate drop-out/exclusion rate of 20%). Both groups will be tested at the time of recruitment

to the study as Pretest 1. The SKY intervention will be given in groups of 10-15 patients and the tests will be performed again within 2 weeks of the first week of yoga (Posttest 1). The control group will be tested at the same time. Posttest 2 will be performed within 2 weeks of completing the 13-week yoga program, using the same parameters. **In addition to daily home practice, there will be weekly follow-up sessions for the SKY group** which will last about 2 hours during which exercises will be performed in a group and questions that may arise related to the practice will be answered. Control subjects will be offered 1-week of yoga classes after the end of the study (ie, after post-test-2)

Below is a brief flowchart of the study timeline:

Week --	Recruitment (3 months prior to the start of yoga)
Week --	Pretest 1 (within 2 months prior to starting yoga)
Week 1-13	SKY intervention (13 weeks)
Week 2-3	Posttest 1 (within 2 weeks of the first week of yoga)
Week 14-15	Posttest 2 (within 2 weeks of the last week of yoga)

Research design and methods:

Aim 1. Determine any change in pain, fatigue and psychological well-being as a result of SKY in PCa patients.

We will assess psychological wellness parameters in the PCa subjects at the time points as described above. This will be done by administering standardized questionnaires which are enumerated below:

1. The Hospital Anxiety and Depression Scale (HADS): A 14-item self-rating scale, measuring anxiety and depression (Zigmond and Snaith, 1983).
2. The EORTC Quality-of-life Questionnaire (EORTC QLQ-C30). A cancer-specific 30-item questionnaire (Aaronson et al., 1993) incorporating 5-functioning scales, a global health-status/QOL scale and symptoms assessment. In addition Functional Assessment of Cancer Therapy-Prostate (FACT-P) questionnaire will be utilized.

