3. The Life Orientation Test – Revised (LOT-R): A 10-item self-report scale, measuring expectations about positive outcome in general (Scheier et al., 1994)
4. 36-item short-form health survey (SF-36) vitality scale, a reliable and valid measure of energy/fatigue in the past month (Stein et al., 1998).
5. Pain will be assessed with the BPI-SF questionnaire (Cleeland and Ryan, 1994).

Aim 2. Assess changes in some physiological parameters in response to SKY.

In addition to the self-report measures described above, it is important to use objective measures to determine if SKY practice results in physiological effects. As reviewed above, previous studies on SKY have indicated various physiological effects, such as positive influence on the immune system, support of the antioxidants system, and effects of gene expression in the circulating immune cells. To evaluate if similar effects are observed in PCa patients, and whether these correlate with the measures in Part 1, venous blood, saliva, and hair will be collected at the three time points and the following tests will be performed:

1. Enzymes indicative of antioxidant status, i.e. Superoxide Dismutase (SOD) and Glutathione peroxidase (GPX) (based on previous studies by Sharma et al., 2003). We will also measure serum 8-isoprostane level, an indicator of oxidative stress.
2. Inflammatory markers, i.e. Interleukin 1 and 6, Tumor Necrosis Factor alpha (TNF α), and C-reactive protein (since these cytokines are important in carcinogenesis and may be modulated by psychosocial intervention therapies).
3. Saliva cortisol taken between 07 and 09 am, as measure of psychophysiological stress (Levine et al., 2007).

4. Hair cortisol, using a 1-inch strand of hair taken from the back of the head, as a measure of psychophysiological stress.
In addition, two epigenetic tests will be performed:
5. RNA will be isolated from the peripheral blood mononuclear cells (PBMCs) and gene expression changes will be assessed as previously done in response to the SKY regimen (Qu et al., 2013).
6. DNA will be isolated from the PBMCs and potential DNA methylation changes in response to SKY regimen.

The levels of these endpoints (1-3) and gene expression profiles will be compared during the different time points as described above.

STUDY FLOW CHART:

Yoga group:

1. **Prestudy evaluations:** Questionnaires, and blood/saliva/hair samples (within 2 months prior to starting Yoga instructions)(Pre-test 1)
2. **Yoga instructions**

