Week 1 – Yoga instruction (3 hours daily for 5 days)
Week 2-13 –Yoga instruction (2 hours on one day each week)
3. **Post-study evaluations (1):** Questionnaires, and blood/saliva/hair samples (within 2 weeks of the first week of yoga)(Post-test 1) (Week 2-3)
4. **Post-study evaluations (2):** Questionnaires, and blood/saliva/hair samples (within 2 weeks of the last week of yoga)(Post-test 2) (Week 14-15)

Control group:

- 1) Prestudy evaluations: Questionnaires, and blood/saliva/hair samples (after consenting) (Pre-test 1)
- 2) Post-study evaluations (1): Questionnaires, and blood/saliva/hair samples (within 6-8 weeks from the pre-test 1 evaluations)(Post-test 1)
- 3) Post-study evaluations (2): Questionnaires, and blood/saliva/hair samples (within 2-4 months after Post-test 1 evaluations)(Post-test 2)
- 4) Control subjects will be offered 1-week of yoga classes after the end of the study (ie, after post-test-2)

Statistical Considerations:

Fifty subjects should be a sufficient sample size because in our previous study with a sample size of 14 subjects we were able to observe statistically significant changes (Qu et al, 2013). Comparisons will be made with the Student's t test. A value of $P < 0.05$ will indicate statistical significance.

Research team:

The main coordinator of the project is [name], Department of Hematology and Medical Oncology, Emory University. The collaborator partners are: [name], Department of Psychiatry; [name], and [name] from Department of Radiation Oncology, Emory University.

Yoga instructions will be provided by Art of Living Center instructors in Atlanta. They have agreed to provide the SKY intervention proposed in this study.

Epigenetic, biochemical and inflammatory marker laboratory tests will be done at [name] Laboratory. [name] has conducted research using similar methodology (testing of wellness parameters, cancer related endpoints, and gene expression) (Kjellgren et al., 2007; Qu et al., 2013) which will facilitate the current work.

Ethical considerations: All work will be done in accordance with the ethical principles of human subject use and the rules of the Institutional Review Board (IRB) at Emory University. All

members of the research team have participated in similar studies before involving human subjects and are thus familiar with all the procedures that are necessary.

REFERENCES

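### Pretest 1 is timed by a different rule in each arm and is nowhere required to precede randomisation, so a baseline taken after allocation is permitted

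*Combined protocol and SAP*

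**What the plan says.** The combined protocol and SAP gives the timing of Pretest 1 in four places.

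- Subjects, study arms text, one rule for everyone: "Both groups will be tested at the time of recruitment".
- Brief timeline in the same section, not split by arm: "Recruitment (3 months prior to the start of yoga", followed by "Pretest 1 (within 2 months prior to starting yoga".
- STUDY FLOW CHART, Yoga group, item 1: "within 2 months prior to starting Yoga instructions)(Pre-test 1".
- STUDY FLOW CHART, Control group, item 1: "Prestudy evaluations: Questionnaires, and blood/saliva/hair samples (after consenting) (Pre-test 1". This has no link to a class date and no upper limit.

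Randomisation appears under Subjects ("The men will be randomly assigned to one of two groups") and again with the total of 50 patients. Neither place dates it relative to consent or Pretest 1. The comparator is "No treatment control". Aim 1 (pain, fatigue and psychological well-being) is measured entirely by questionnaire. Statistical Considerations names Student's t test but does not say whether it is applied to changes or to post-test values, or within or between arms.

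**The concern.** A baseline is protected from the effect of allocation only if it is completed before anyone knows the arm. Here the document that sites would work from gives each arm its own Pretest 1 rule, the rules disagree with the text under Subjects, and nothing places Pretest 1 ahead of randomisation.

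The setting makes this matter. The control is no treatment, so every man knows his arm. Entrants must be interested in yoga-type exercises and willing to practise daily, so news of the allocation may be welcome to some and disappointing to others. Mood, fatigue and pain ratings given after that news could differ by arm before any yoga has taken place. The shift would carry into any change from Pretest 1. Baselines taken under different rules would also lie at different distances from consent. If allocation did come first, men who withdrew on learning their arm would have no baseline at all. None of this can be repaired in the analysis afterwards.

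**Working it through.** **Sample size.** The plan's own figure reproduces: 20 / (1 − 0.20) = 25 per arm, 50 in total. No effect size, SD or power is given, and the point does not depend on this figure.

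**The Pretest 1 rules side by side** (months before the class starts)

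| Source | SKY | Control |
|---|---|---|
| Subjects, text | at recruitment | at recruitment |
| Subjects, timeline | 2 to 0 (recruitment at 3) | 2 to 0 (recruitment at 3) |
| Study flow chart | 2 to 0 | any time after consent |

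1. *Within the Subjects section.* A man recruited 3 months before class and tested at recruitment is tested 3 − 2 = 1 month too early for the timeline row. For him the two rules cannot both be met.

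2. *Between arms in the flow chart.* Take two men who consent on the same day, 3 months before class. The control man may be tested that day. The SKY man may be tested no earlier than 2 months and no later than 0 months before class. If the control man is tested at once, the gap is between 3 − 2 = 1 month and 3 − 0 = 3 months. This is what the rules allow. They do not require it, because the control rule sets no latest date.

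3. *Is allocation needed to apply the rules?* No. A visit after consent, before randomisation and no more than 2 months before class meets both flow-chart lines. Allocation matters only if early consenters are tested promptly when they are controls and deferred when they are SKY.

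4. *Order relative to randomisation.* No section states it. Both orders are compatible with the text.

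**Illustration of the consequence.** Assumptions, none of them from the plan: a two-sided t test on change from Pretest 1, 20 men per arm, no true effect, and a pre-post correlation of 0.5.

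- SD of change = √[2(1 − 0.5)] = 1 outcome SD.
- Change = post-test − Pretest 1, so a baseline difference of b between arms that is absent at post-test moves the difference in change by b, with opposite sign.
- Noncentrality = b × √(20/2), with 38 degrees of freedom and critical value 2.024.

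| Assumed shift b (SD) | Noncentrality | Chance of P < 0.05 |
|---|---|---|
| 0 | 0 | 5.0% |
| 0.1 | 0.316 | 6.1% |
| 0.2 | 0.632 | 9.5% |
| 0.3 | 0.949 | 15.2% |

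These rates count rejections in either direction. If the t test compares post-test values alone, Pretest 1 does not enter and this route contributes nothing.

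**The case against.** A reader might infer that rules written by arm can be applied only once the arm is known, and so that the plan puts Pretest 1 after randomisation. The documents do not support that. One visit can satisfy both flow-chart rules before allocation, and testing both groups at recruitment fits a pre-randomisation baseline.

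There is also an innocent explanation for the layout. Control men have no class date, so their visits have to be anchored to something else. The control Posttest 1 window ("within 6-8 weeks from the pre-test 1 evaluations)(Post-test 1") fits a shared calendar: a common Pretest 1 five weeks before class, plus a SKY Posttest 1 about 1 to 3 weeks after the class starts, gives 6 to 8 weeks. The author may have had one schedule in mind for both arms.

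Two further objections have force. The plan does not specify a change-score analysis, and the shift sizes are assumed. The direction is unknown too: if men told they have yoga report feeling better at baseline, or controls report feeling worse, the change comparison would hide a benefit rather than create one.

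All of this stands, and it limits the claim. It does not remove the contradiction between the Subjects text, its timeline and the flow chart, and it does not supply the missing order. A shared calendar may have been intended, but the written SKY rule accepts any Pretest 1 in a two-month span. With 1 month = 4.35 weeks, that allows from 1 week to 2 × 4.35 + 3 = 11.7 weeks between Pretest 1 and Posttest 1, against 6 to 8 weeks for controls.

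**Conclusion.** The point holds in a limited form. The Pretest 1 rules contradict one another, differ by arm in the flow chart, and are nowhere tied to a time before randomisation. A post-allocation baseline timed differently by arm is therefore permitted. It is not shown to be planned.

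The possible gap between arms is up to 3 months for men consenting 3 months before class, if the control man is tested at consent. Any bias could create or mask an effect, and it reaches only analyses that use change from Pretest 1. The error rates of about 6%, 9% and 15% illustrate how sensitive a trial of this size would be under assumed shifts and a change-score analysis; they are not estimates for this trial.

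This is more than a missing detail, because the stated rules conflict and the control arm is unblinded with self-reported outcomes. It should be settled before enrolment.

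**What to change.** Replace the two arm-specific Pretest 1 lines in the study flow chart with one sequence for both arms:

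1. Consent.
2. Pretest 1, meaning questionnaires and all samples, within one common window before the planned class start. Use the same class date as the reference for men who will later be controls.
3. Randomisation, only of men whose Pretest 1 is complete.

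Then amend the Subjects text and its timeline so that testing at recruitment, recruitment at 3 months and Pretest 1 within 2 months all agree with that sequence.

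The cost is revised wording and scheduling, with no added visits or tests. Men who consent early will wait longer for Pretest 1 and to learn their arm. Some may withdraw in that interval, but they would do so before randomisation, so the comparison between arms would not be affected.

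### The only named method is Student's t test with no stated contrast; name SKY versus control as the comparison and adjust it for Pretest 1

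*Combined protocol and SAP*

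**What the plan says.** The analysis plan is two sentences under Statistical Considerations: "Comparisons will be made with the Student's t test", and a significance threshold of P < 0.05. The form of the test (paired or two-sample), the arms or visits compared, and the outcome (posttest value or change) are not given.

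Other wording on comparisons is limited:

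- **Research design and methods, Aim 2:** "The levels of these endpoints (1-3) and gene expression profiles will be compared during the different time points as described above". No arm is named. Items 1–3 cover the antioxidant and oxidative-stress markers, the inflammatory markers and saliva cortisol. Hair cortisol is item 4 and falls outside the sentence.
- **Specific Aims and Aim 2:** the physiological measures are to be related to the questionnaires ("compare these with those from Part 1"; "whether these correlate with the measures in Part 1"). This is a link between outcomes, not a treatment contrast.
- **Aim 1 questionnaires:** no contrast is stated.

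The Subjects section describes a controlled design: "The men will be randomly assigned to one of two groups", namely no treatment or SKY. On measurement it says "Both groups will be tested at the time of recruitment" and, for Posttest 1, "The control group will be tested at the same time". It aims for 20 men per group and recruits 25 to allow for 20% drop-out or exclusion.

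**The concern.** The wording allows two quite different analyses.

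**Visits compared within SKY.** The control arm is then unused, and any change that would have happened anyway is credited to SKY. Entry requires radiotherapy to have ended at least two months ago, with no upper limit, so some natural change is possible. The documents give no rate.

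**Arms compared at a visit.** Drift common to both arms then causes no bias. But the plan does not say whether the outcome is the posttest value or the change from Pretest 1, and it does not mention baseline adjustment. With about 20 men per arm these choices affect power, and leaving them open allows them to be made after the data are seen.

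**Working it through.** **Inputs from the documents.** 20 completers per arm; P < 0.05 (taken as two-sided, since sidedness is not stated); Pretest 1 and both posttests collected in both arms.

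**Assumptions, because the documents give no values.** Outcome SD set to 1; Pretest–Posttest correlation r = 0.3, 0.5 or 0.7; natural drift of 0.1, 0.2 or 0.3 SD.

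**The plan's own figure.** 20/(1 − 0.20) = 25 per arm, 50 in total, which agrees with the protocol. The target of 20 cannot be re-derived, because no effect size, SD or power is given.

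**1. Paired t test within SKY, no SKY effect.** The SD of the change is √(2(1 − r)). The noncentrality is drift × √20 / √(2(1 − r)) on 19 df. For drift 0.2 and r = 0.5 it is 0.2 × 4.472 / 1 = 0.894. Probability of a significant result:

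| Drift | r = 0.3 | r = 0.5 | r = 0.7 |
|---|---|---|---|
| 0.1 SD | 6.5% | 7.1% | 8.5% |
| 0.2 SD | 11.1% | 13.6% | 19.5% |
| 0.3 SD | 19.0% | 24.7% | 37.6% |

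For comparison, simulated between-arm tests with a 0.3 SD drift in both arms and no effect rejected in 4.85% to 5.04% of trials, whether on posttest values, change scores or by ANCOVA.

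**2. Between-arm options, 20 per arm.** The variance of the estimated difference is (2/20) × f, where:

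- posttest values: f = 1, 38 df;
- change scores: f = 2(1 − r), giving 1.4, 1.0 and 0.6, 38 df;
- ANCOVA: f = (1 − r²)(1 + 1/36), giving 0.935, 0.771 and 0.524, 37 df. The second factor is the expected cost of estimating the slope.

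Noncentral t results:

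| | r = 0.3 | r = 0.5 | r = 0.7 |
|---|---|---|---|
| **Detectable difference, 80% power (SD)** | | | |
| Posttest values | 0.91 | 0.91 | 0.91 |
| Change scores | 1.08 | 0.91 | 0.70 |
| ANCOVA | 0.88 | 0.80 | 0.66 |
| **Power at an assumed 0.8 SD** | | | |
| Posttest values | 69% | 69% | 69% |
| Change scores | 55% | 69% | 89% |
| ANCOVA | 72% | 80% | 93% |

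Simulated ANCOVA at 0.88, 0.80 and 0.66 SD gave power of 0.801, 0.804 and 0.800, which confirms the formula.

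**3. Where adjustment stops paying.** ANCOVA and posttest values have the same detectable difference at r of about 0.17. At r = 0 ANCOVA has 68.1% power at 0.8 SD against 69.3%, a loss of about one point.

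**The case against.** **The design already implies an arm comparison.** Men are randomised to SKY or no treatment, the control group is tested alongside, and Aim 1 speaks of change as a result of SKY. The false-positive figures also need an assumed drift, and men long past radiotherapy may be stable. This stands to the extent that the within-SKY analysis is not shown to be the plan. It does not supply the missing contrast, and the Aim 2 wording refers to time points rather than arms.

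**ANCOVA is a preference, not a correction.** A between-arm t test is valid. At r = 0.3 the gain over posttest values is 0.03 SD. At r = 0.7 the gain over change scores is 0.70 to 0.66 SD. All of this is true. But r is unknown and will differ by endpoint. Over the range studied ANCOVA beats both t tests, and below r of about 0.17 it loses very little to posttest values.

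**Group delivery weakens the 5% claim.** The Subjects section says "The SKY intervention will be given in groups of 10-15 patients", so outcomes may be correlated within groups. With two SKY groups of 10, 20 unclustered controls, a group effect arising after baseline and an assumed intraclass correlation of 0.05, simulated ANCOVA rejects in about 8%, 8.5% and 10% of null trials at r = 0.3, 0.5 and 0.7, against just under 8% for the posttest t test. This stands. Clustering affects any unclustered between-arm test and needs its own treatment, but it inflates ANCOVA more when r is high.

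**Control visits may not be aligned.** The study flow chart times control posttests from each man's own earlier visits (6–8 weeks, then 2–4 months), whereas the Subjects section tests controls together with SKY. If the flow chart governs, drift need not be common to both arms. Those passages must be reconciled. Naming the contrast does not settle this.

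**Conclusion.** The concern holds. Student's t test is the only method named, its contrast is not stated, and no section plans a SKY-versus-control comparison or an adjustment for Pretest 1. It should be fixed.

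The essential part is the arm contrast. Without it, a within-SKY test remains possible and would carry a false-positive rate of 6–9%, 11–20% or 19–38% for a drift of 0.1, 0.2 or 0.3 SD. The baseline adjustment is a secondary gain in precision: against posttest values it cuts the detectable difference by 0.03, 0.11 and 0.25 SD at r = 0.3, 0.5 and 0.7.

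These sizes rest on assumed r and drift, 20 completers per arm and a two-sided 5% level. The 5% rate for the between-arm test also assumes independent men and a drift common to both arms.

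**What to change.** Replace the sentence naming the t test with wording such as:

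> *Each questionnaire score and individual biomarker is compared between the randomised arms, as assigned, by ANCOVA at Posttest 2 (Posttest 1 secondary) with the Pretest 1 value as covariate. The adjusted SKY-minus-control difference is reported with a 95% CI. Within-arm changes are descriptive only.*

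The priority given to Posttest 2 is a proposal. The documents do not rank the two posttests, so the sponsor should confirm the choice before any data are examined.

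The sentence does not cover gene expression, which the protocol refers to the methods of an earlier study, or DNA methylation; both need their own method. Nor does it deal with clustering from group delivery, the timing of control visits, the choice of a primary endpoint or the handling of drop-outs.

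**Cost:** one sentence of SAP wording, one degree of freedom and slightly more analysis work. No additional men, visits or samples are needed, because Pretest 1 and both posttests are already collected in both arms.

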Another study found significantly lower levels of blood lactate in practitioners of SKY compared with the control group. Conversely, the levels of superoxide dismutase (SOD), catalase, and glutathione, three major defenses against oxidative stress, were all found to be significantly higher in SKY practitioners compared with the control group (Sharma et al., 2003). These data suggest that people who practice SKY have an improved antioxidant status and defense against oxidative stress.

Various additional studies indicate that SKY results in improved physical and psychological health. For example, there are interesting findings on the effects of SKY on brain function, indicative of a state of wakeful alertness (Bhatia et al., 2003). In addition, there appears to be strengthening of the immune system, as measured by increases in natural killer (NK) cell number, in both healthy people, but also in cancer patients (Kochupillai et al., 2005). Furthermore, SKY has been shown to be effective in post-traumatic stress disorder (Carter et al., 2013) and in a randomized trial **[name]** and co-workers found that it affected the circulating immune cells at the level of gene expression (Qu et al., 2013).

The goal of this proposal is to systematically study the possible impact of SKY on PCa patients. The studies will include not only psychological assessment through self-report questionnaires on pain, fatigue and psychological well-being, but also objective measures on basic physiological parameters, including the stress hormone cortisol and cytokine IL-6. **Our hypothesis** is that there would be a measurable effect of SKY on psychological distress in PCa patients on the

parameters to be tested, and that this will correlate with favorable changes in physiological parameters that may impact disease progression.

Our preliminary data from two clinical trials we conducted in students (Kjellgren et al, 2007) and healthy volunteers (Qu et al, 2013) support our hypothesis (see above, studies by [name] and co-workers, as referenced in Kjellgren and Qu papers). There was decreased anxiety, depression and stress in one study, and improved physiologic changes in the other. These preliminary results give us confidence that the proposed study will show the hypothesized improvements in the health status and physiological parameters of patients with PCa.

Specific Aims:

This study will have two parts:

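### Every comparison is judged at P<0.05 with no primary endpoint, time point, contrast or multiplicity control; at roughly 28 to 44 tests the familywise error is far above 5%

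*Combined protocol and SAP*

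**What the plan says.** The Statistical Considerations section justifies the sample size by an earlier 14-subject study, then says "Comparisons will be made with the Student's t test" and "A value of $P < 0.05$ will indicate statistical significance". It does not say whether tests are paired or unpaired, one- or two-sided, or which contrast is meant.

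No other section of the available text ranks the outcomes. The hypothesis is that "there would be a measurable effect of SKY on psychological distress in PCa patients", but it goes on to cover all the parameters tested. The first Specific Aim is: "Determine any change in pain, fatigue and psychological well-being as a result of SKY in PCa patients". Under Research design and methods, Aim 1 lists six questionnaires: HADS, QLQ-C30, FACT-P, LOT-R, SF-36 vitality and BPI-SF. The QLQ-C30 is described as "incorporating 5-functioning scales, a global health-status/QOL scale and symptoms assessment".

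Aim 2 lists nine biomarkers, gene expression and DNA methylation. Of these it says "The levels of these endpoints (1-3) and gene expression profiles will be compared during the different time points as described above", and for expression that "gene expression changes will be assessed as previously done in response to the SKY regimen". All measures are taken at Pretest 1, Posttest 1 and Posttest 2, and neither post-test is given priority.

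**The concern.** A 5% threshold controls the error of one pre-specified test. Applied separately to dozens of outcomes and visits, it leaves a large chance that something is significant even if SKY has no effect on anything. With no endpoint, visit or contrast fixed beforehand, any of those results could be put forward as the trial's finding, and a reader could not tell it from chance. This cannot be repaired credibly once the data have been seen.

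**Working it through.** **The plan's own figures.** The recruitment target reproduces: "20 subjects are aimed at in each group" with 20% drop-out gives 20 / (1 − 0.20) = 25 per arm, 50 in total. The 20 per arm cannot be derived, because no effect size, SD or power is stated. The only error rate given is 0.05 per test.

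**Counting the tests.** Assume one two-sided, unpaired SKY-versus-control test per measure at each of two post-tests.

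- Lower count: six questionnaires at one score each, plus the eight markers in Aim 2 items 1–3 (SOD, GPX, 8-isoprostane, IL-1, IL-6, TNF-alpha, CRP, saliva cortisol). That is 14 × 2 = 28.
- Fuller count: HADS 2 scores, QLQ-C30 7 (five functioning, one global, symptoms counted once) and the other four 1 each give 13; nine markers with hair cortisol give 22. That is 22 × 2 = 44.

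Further subscales, within-arm changes, biomarker–symptom correlations and the omics are left out of both counts.

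**Independent tests, no true effect.** The chance of at least one P<0.05 is 1 − 0.95^m. For a false result in SKY's favour (nominal 2.5%) it is 1 − 0.975^m.

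- m = 28: 1 − 0.95^28 = 76.2%; 1 − 0.975^28 = 50.8%.
- m = 44: 1 − 0.95^44 = 89.5%; 1 − 0.975^44 = 67.2%.

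Expected false positives are 28 × 0.05 = 1.4 and 44 × 0.05 = 2.2. Half of these, 0.7 and 1.1, would favour SKY.

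**Correlated tests.** The documents give no correlations, so a common correlation ρ between all test statistics is assumed. With c = 1.96, u standard normal with density φ, and Φ the normal distribution function, the chance of at least one two-sided rejection is

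1 − ∫ φ(u) [Φ((c − √ρ·u)/√(1−ρ)) − Φ((−c − √ρ·u)/√(1−ρ))]^m du.

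For SKY's favour, the second Φ term is dropped, with all outcomes oriented so that a positive value is favourable.

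| ρ | 28 tests, any | 44 tests, any | 28 tests, favours SKY | 44 tests, favours SKY |
|---|---|---|---|---|
| 0.2 | 70.0% | 83.4% | 38.9% | 49.2% |
| 0.3 | 64.1% | 77.2% | 33.8% | 42.2% |
| 0.5 | 49.1% | 59.3% | 24.7% | 30.0% |
| 0.7 | 33.0% | 38.8% | 16.5% | 19.4% |

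Simulating actual t tests with 20 per arm (20,000 trials) agrees. At ρ = 0.2 and 0.7 the two-sided figures are 70.6% and 33.5% for 28 tests, and 83.6% and 40.3% for 44. In SKY's favour they are 39.6% and 16.4%, and 49.7% and 20.1%.

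**Sensitivity to the correlation structure.** A second simulation let the between-visit correlation differ (assumed factor 0.6). For 28 / 44 tests it gave 65% / 78% at between-outcome correlation 0.3, 54% / 66% at 0.5, 40% / 48% at 0.7 and 25% / 27% at 0.9.

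**Omics.** No platform or feature count is given. If P<0.05 were applied feature by feature, each 1,000 null features (an assumption) would give about 1,000 × 0.05 = 50 false calls.

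**The case against.** The plan does not itself specify 28 or 44 tests. The sentence about comparing levels across time points can be read as within-subject change rather than a between-arm test. How the questionnaires will be scored is not stated, and that sentence does not cover hair cortisol. This makes the count illustrative. It does not rescue the rule: within-arm testing would add tests, and 44 is not an upper bound.

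The percentages depend on the correlation model, as the two simulations show, and the figures in SKY's favour also assume that outcomes correlate positively in the favourable direction. The two aims could fairly be treated as separate families. Aim 1 alone, six scores at two visits, is 12 tests: 1 − 0.95^12 = 46% if independent, 32% at correlation 0.5 and 23% at 0.7. Six scores at one visit give 26%, 21% and 16%. The independent-case 76% and 90% are therefore the least favourable framing, but the most favourable is still about three times nominal.

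The hypothesis does put psychological distress first. That is a reason for choosing a primary, not a named endpoint. Gene expression methods are deferred to a cited study that cannot be checked here, so the omics arithmetic is conditional and the conclusion does not rest on it. Methylation has no such deferral.

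Finally, this is a small one-year study for which an exploratory label might suffice. But only the epigenetic work is called pilot, in the budget. The plan states a hypothesis, expects to confirm it and sets a significance threshold.

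**Conclusion.** The concern holds and must be fixed. Followed as written, the rule gives unreliable significance claims. Under no true effect, the chance of at least one is 76% to 90% for 28 to 44 independent tests, and 33% to 83% across those counts at common correlations of 0.2 to 0.7. The chance of at least one in SKY's favour is 16.5% to 67% across the same cases, against a nominal 2.5%. These sizes rest on one between-arm test per measure and post-test and on assumed correlations. The direction does not: every count and correlation examined gives a familywise error well above 5%. The statement that no primary or multiplicity rule exists covers the available text, which includes the aims, methods and statistical sections where one would be expected.

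**What to change.** Before any outcome data are seen, add a short analysis section that does the following.

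1. Names one primary endpoint, time point and contrast consistent with the distress hypothesis. For example: HADS total at Posttest 2, SKY versus control, ANCOVA adjusted for the Pretest 1 value, two-sided alpha 0.05.
2. Only if that is significant, tests one pre-named BPI-SF pain score and SF-36 vitality at Posttest 2 in the same way, with Holm's correction. This holds familywise error at 5% over the three tests.
3. Reports all other scores, biomarkers and Posttest 1 results as exploratory estimates with 95% confidence intervals and no significance claim.
4. Applies a Benjamini-Hochberg false discovery rate of 5% to any feature-wise expression or methylation testing, and states the platform and number of features.

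The choice of primary, and whether a biomarker belongs in the hierarchy, is the sponsor's. If the sponsor regards the whole trial as exploratory, the alternative is to say so and drop the significance rule throughout.

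The cost is some text and a power statement, with no new data, and fewer results that can be called significant. At 20 evaluable per arm, an unadjusted t test on the primary has 80% power only for a standardised difference of 0.91. Baseline adjustment lowers this to 0.909 × √(1 − 0.5²) = 0.79, or 0.909 × √(1 − 0.7²) = 0.65, for assumed pre–post correlations of 0.5 or 0.7. The first Holm step (alpha 0.025, unadjusted) needs 1.01. Bonferroni across all tests would be costlier: 0.05/28 = 0.00179 needs 1.34, and 0.05/44 = 0.00114 needs 1.39.
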